## 6.5.2 Unblinding

The blind should be broken for all SAE IND safety reports that are judged to be expedited reports for submission to FDA. The unblinding procedures and follow-up will be performed in accordance with the protocol and the CRO's standard operating procedures (SOPs). The blind should not be broken at the study site level except in a medical emergency (where knowledge of the study medication received would affect the treatment of the emergency). For a medical emergency, the blind must only be broken following discussion on a case-by-case basis, at the discretion of the Investigator/treating physician/Sponsor.

If the blind is broken, the date, time, and reason must be recorded in the subject's source record, eCRF, and any associated AE report. If an Investigator, site personnel performing assessments, or subject is unblinded, the unblinding incident and unblinded subject must be listed as a major protocol deviation. A subject for whom the blind is broken will discontinue study medication and be scheduled for a safety follow-up visit and then discontinued from the study. The subject will be encouraged to stay in the study until the AE is resolved or stabilized. All Investigators and the IRB will receive blinded reports. However, on the request of the IRB, the Sponsor will send unblinded reports directly to the IRB.

### 6.6 Prior and Concomitant Therapy and Procedures

Chronic medications being used at the time of the Screening and Baseline Visit, with the exception of those specified as prohibited, may be continued at the discretion of the investigator. History of medications, therapies, and procedures is collected from the prior 6-month period for determination of eligibility. Only medications, therapies and procedures in use during the study should be entered on the eCRF.

New medications used after baseline required for another medical condition, that in the opinion of the investigator will have no material impact on the study, are permitted. The addition of such a new medication during the study will be documented as a concomitant medication and the associated medical need must be recorded as an AE, if applicable.

All medications (topical, oral, prescription, over-the-counter, and herbal medications) and medical therapies or procedures that are used during the study for other diseases/conditions must be recorded on the eCRF.

Subjects will only be allowed to use a non-medicated investigator-approved gentle cleanser, facial wash, sunscreen, and/or non-comedogenic moisturizer with SPF, and make-up.

Subjects should be instructed to refrain from making any significant change in the use of consumer products during the course of the study. All consumer products used on the face will be recorded at baseline and any changes will be captured in the source documents and eCRF. The name and the date that the new product was started will be recorded.

See Table 2 for a list of medications and procedures that are prohibited during the study.

## 6.7 Study Restrictions

Only the assigned study product and non-medicated investigator-approved sunscreen and moisturizer with SPF, gentle cleanser, face wash, and non-medicated make-up should be applied to the face during the study.

Subjects must be willing to comply with sun avoidance measures for the face [and chest and/or back (including shoulders), if applicable], including use of investigator-approved non-medicated sunscreen and/or hats, have limited sun exposure time, and have no tanning bed use.

### 7 STUDY PROCEDURES AND EVALUATIONS

#### 7.1 Informed Consent Process

Informed consent must be obtained before a subject can participate in the study, prior to performing any study related procedures and before withdrawal of any therapies prohibited during the study. The investigator must discuss the study fully with the subject (and legal guardian, as applicable). Subjects must demonstrate their willingness to participate in the study and comply with the study procedures by giving written informed consent or written assent, as applicable. The consent form and 'Information and assent' form must be signed and dated by the subject or legal guardian, as applicable. A copy of the consent form (and 'Information and assent' form, as applicable) must be given to the subject and/or legal guardian, and the date of the consent process and who conducted the consent process must be documented in the source documents.

## 7.2 Screening

A separate Screening Visit (Visit 1) may be performed when a washout period is required or for scheduling purposes. Alternatively, Visits 1 and 2 may be combined if no washout period is required. The screening number, date of visit, date of consent, reason for screen failure, and study status (screen failure) will be captured in the eCRF for every screen failure subject. The Baseline Visit 2 must occur no later than 60 days after the Screening Visit. Medical history and acne history should be collected for the prior 1-year period and concomitant medications, therapies, and procedures collected for the prior 6-month period. Only ongoing medical conditions and ongoing concomitant medications should be entered on the eCRF. Acne history will be collected and recorded in the eCRF.

A screen failure is a subject who received information about the study, including signing an informed consent and possibly performing some study-related procedures, but was not randomized and/or did not use study product.

## 7.3 Demographic and Baseline Characteristics

Demographic variables include age (computed from date of birth and Baseline Visit date), race, ethnicity, and sex. Baseline characteristics are the baseline values for the efficacy variables – inflammatory lesion count, non-inflammatory lesion count, and IGA.

# 7.4 Fitzpatrick Skin Type Assessment

The Fitzpatrick skin scale (Fitzpatrick, 1988; Table 3) classifies a person's complexion and tolerance of sunlight. It is commonly used by many practitioners to determine how someone will respond or react to facial treatments, and how likely they are to get skin cancer.

The Fitzpatrick Classification Scale will be performed at Day 1 (Baseline) prior to the first application of study medication and will be recorded in the subject's source document and CRF.

Skin Type	Skin Color	Characteristics
I	White; very fair; red or blond hair; blue eyes; freckles	Always burns, never tans
II	White; fair; red or blond hair; blue, hazel, or green eyes	Usually burns, tans with difficulty
III	Cream white; fair with any eye or hair color; very common	Sometimes mild burn, gradually tans
IV	Brown; typical Mediterranean Caucasian skin	Rarely burns, tans with ease
V	Dark Brown; mid-eastern skin types	very rarely burns, tans very easily
VI	Black	Never burns, tans very easily

**Table 3: Fitzpatrick Classification Scale** 

### 7.5 Efficacy Assessments

The investigator will be responsible for all clinical evaluations, with best attempts made to assign the same evaluator for a subject throughout the study to obtain consistency in grading scores and measurements.

Efficacy assessments will be conducted using IGA for overall disease severity and inflammatory and non-inflammatory lesion counts on the face. The IGA should always be done prior to lesion counts.

# 7.5.1 Investigator's Global Assessment (IGA) of the Face

The IGA scale to be used in the study is a measure of static evaluation of qualitative overall acne severity. IGA is an ordinal scale with five severity grades (reported only in integers, e.g., 0 to 4). Each grade is defined by a distinct and clinically relevant morphologic description to minimize inter-observer variability (Table 4). The grades on the scale have been sufficiently defined to appropriately and unambiguously represent each severity grade on the scale. The investigator is required to perform IGA scoring at each visit. The IGA should always be done prior to lesion counts.

Grade	Description
0	Clear skin with no inflammatory or non-inflammatory lesions
1	Almost clear; rare non-inflammatory lesions with no more than rare papules
2	Mild severity; some non-inflammatory lesions with no more than a few inflammatory lesions (papules/pustules only, no nodular lesions)
3	Moderate severity; up to many non-inflammatory lesions and may have some inflammatory lesions, but no more than one small nodular lesion
4	Severe; up to many non-inflammatory and inflammatory lesions, but no more than a few nodular lesions

**Table 4: IGA Scale for Facial Acne Vulgaris** 

### 7.5.2 Lesion Counts of the Face

Non-inflammatory lesions (closed comedones and open comedones), inflammatory lesions (papules and pustules), and nodulocystic lesions (nodules and cysts) on the face (above the mandibular line), including the nose, will be counted and recorded separately at each visit from Screening/Baseline through Week 12. Non-inflammatory lesions of acne are the open (blackheads) or closed (whiteheads) comedones. Closed comedones may be more difficult to detect visually and may require stretching of the skin to aid in visualization. Inflammatory lesions are divided into papules, pustules, and nodules/nodulocystic lesions, depending on the severity and location of the inflammation within the dermis. Nodulocystic lesions will be counted separately from inflammatory lesions of papules and pustules. The papules and pustules have surrounding halos of erythema allowing for their characterization as inflammatory. Nodules are typically erythematous and often tender and/or painful. Additionally, they are deepseated in the skin (i.e., centered in the dermis or subcutis). Nodules have been defined as being greater than 5 mm in diameter. The borders of these lesions may be difficult to determine because of the associated erythema/inflammation. The investigator/evaluator should use standard, good lighting to visualize lesions and a systematic counting procedure to ensure consistent and accurate counts.

## 7.5.3 Lesion Counts of the Chest and/or Back (including shoulders)

At selected site(s), for subjects who have acne lesions on their chest and/or back (including shoulders), lesion counts will be assessed separately for these areas.

Non-inflammatory lesions (closed comedones and open comedones), inflammatory lesions (papules and pustules), and nodulocystic lesions (nodules and cysts) on the chest and/or back including shoulders (if applicable) will be counted and recorded separately at each visit from Baseline through Week 12. Nodulocystic lesions will be counted separately from inflammatory lesions of papules and pustules. The back area is from most prominent cervical spinous process superiorly to the superior aspect of iliac crest inferiorly and the shoulder area will also be included. The chest area is from the manubrium of the sternum superiorly to the xiphiod process inferiorly. The lesion types are as described above. The investigator/evaluator should use standard, good lighting to visualize lesions and a systematic counting procedure to ensure consistent and accurate counts.

## 7.5.4 Cardiff Acne Disability Index (CADI)

The CADI is a short 5 item questionnaire that will be conducted by all subjects at Baseline, Week 4, 8, and 12. The questionnaire rapidly assesses the disability caused by the acne. It consists of 5 questions. The scoring for each question is done from 0 to 3 (a=3, b=2, c=1, d=0). The CADI score is calculated by summing the score of each question resulting in a possible maximum of 15 and a minimum of 0. The higher the score, the more the quality of life is impaired.

The CADI questionnaire is provided in Appendix 2.

### 7.6 Safety Assessments

Safety assessments include vital signs, local cutaneous tolerance evaluation of the treated skin, and AEs. Vital signs (blood pressure and pulse) will be collected at each visit. A physical examination will be performed at Baseline (Day 1) and at Week 12. Urine pregnancy tests for all female subjects (regardless of childbearing potential) will be conducted at Screening and Baseline (Day 1) and at each subsequent visit. Adverse events will be collected by spontaneous reports from subjects (either verbal or recorded in the subject diary), by directed questioning of subjects, and by observation (see Section 8 for details about AEs). Adverse events, whether believed by the investigator to be related or unrelated to treatment, will be recorded on the eCRF.

At Visits 2 through 5 the investigator will assess local cutaneous tolerance by examining treated areas for clinically significant non-lesional erythema, peeling, and dryness that will be graded as shown below (Table 5, Table 6, Table 7) and recorded on the eCRF. Assessments will be recorded separately for the face and (if applicable) chest and/or back (including shoulders) for selected site(s). The investigator will also ask the subject if any stinging (Table 8), burning (Table 9), or itching (Table 10) has occurred on the face and chest and/or back (including shoulders), if applicable since the last visit (for Visit 2 in the last 2 weeks). Visit 2 assessments are made prior to first application. An AE should be recorded if the severity is worse than at Baseline. In addition, overall cutaneous tolerance should be graded at the Week 12 visit, or the last visit if earlier, using the grading shown in Table 11. The local cutaneous tolerance signs and

symptoms will be assessed separately for the face and chest and/or back (including shoulders), if applicable, for selected site(s), using the same scales below.

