**Table 2: Washout Periods (Prior to Baseline - Visit 2)** 

Product	Washout Period	During Study
Topical acne treatments (retinoids, antibiotics, benzoyl peroxide, azelaic acid, resorcinol, salicylates, α-hydroxy/glycolic acid), or other topical facial medication (antifungals, steroids, anti-inflammatories) on the treatment area, including prescription and non-prescription products	14 days	Prohibited
Systemic corticosteroids, systemic acne treatments including systemic antibiotics used for acne treatment, photosensitizing agents (thiazides, phenothiazines), spironolactone, flutamide, or immunosuppressant drugs	30 days	Prohibited
Other investigational product or device		
Systemic antibacterials	Allowed except systemic antibiotics used for acne treatment which will require a 30- day washout period	Up to 10 days allowed for indications other than acne
Facial procedures such as chemical peel, laser treatment, photodynamic therapy, acne surgery, cryodestruction or chemodestruction, x-ray therapy, intralesional steroids, dermabrasion, or depilation (except eyebrow shaping)	30 days	Prohibited [Eyebrow shaping (except for tweezing) is prohibited during the study]
Systemic retinoid (including high dose vitamin A > 10,000 units per day)	180 days	Prohibited

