**Table 7: Scoring of Dryness** 

Severity	Score	Description
None	0	No dryness
Mild	1	Slight barely perceptible fine superficial scale
Moderate	2	Clearly perceptible fine scale giving skin a powdery appearance
Severe	3	Marked roughness, cracked skin with fissures

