### 7. Conduct clinical assessments:

- a. IGA for the face (Table 4). IGA assessments should always be done prior to lesion counts.
- b. Count inflammatory and non-inflammatory lesions on the face and, if applicable, on chest and/or back (including shoulders) for selected site(s). These counts should be recorded separately for the face and, if applicable, chest and/or back (including shoulders) for selected site(s).
- c. Local cutaneous safety evaluation for dryness, non-lesional erythema, and peeling. The investigator should also ask the subject if any burning, stinging, or itching has occurred on the face in the last 14 days. These evaluations should be recorded separately for the face and, if applicable, chest and/or back (including shoulders) for selected site(s).
- 8. Administer the CADI questionnaire.
- 9. The independent third party study medication dispenser will perform the following procedures:
  - a) Assign a subject number using the subject kit #. Randomize subject by using the lowest available number of study kit at the study site.
  - b) Weigh and then dispense 2 bottles or 1 tube of study product (depending on the treatment assignment) to subjects. For the selected site(s) who will enroll subjects with acne on the chest and/or back, weigh and dispense 4 bottles or 2 tubes of study product. The tear-off panel is to be affixed to the source document and filed in subject's chart. Instruct subject on study product use. Review the Subject Instructions with subject. Instruct subject to not discuss study product with Investigator or other study staff.
  - c) Supervise the first application of study product at the site to ensure that it is done correctly.
  - d) Remind subject to bring all bottles or tubes of study product to next visit.
  - e) Dispense and review use of diary. Remind subject to report missed applications and/or potential AEs as well as any medication used in the diary and to bring diary to each visit.
- 10. Schedule next visit.
- 11. Complete eCRF for randomized subjects. For every screen failure subject, record the subject number, date of visit, date of consent, reason for screen failure, and study status (screen failure) in the eCRF.

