### 8 ADVERSE EVENTS

Adverse events will be collected by spontaneous reports from subjects, either verbal or recorded in the subject diary, by directed questioning of subjects, and by observation.

The most common frequently reported adverse reactions during clinical trials with tazarotene cream 0.1% for the treatment of acne were desquamation, dry skin, erythema, and burning sensation, occurring in 10% to 30% of subjects. Adverse reactions occurring in 1% to 5% of treated subjects included pruritus, irritation, face pain, and stinging.

The investigator is to pay special attention at each visit to any signs of clinically significant dryness, non-lesional erythema, and peeling and report as an AE subsequent to the Baseline Visit if worse than at Baseline.

An AE is any untoward medical occurrence in a subject participating in a clinical trial. The event does not necessarily have to have a causal relationship with the study product. An AE can therefore be any sign, symptom, or disease, or any worsening of an existing sign, symptom, or disease, whether or not considered related to the study product or trial procedures, including injuries.

Any medical condition that is present at the time of Screening or Baseline should be considered as medical history and reported on the medical history eCRF and should not be reported as an AE except for AEs observed at the Baseline Visit due to study procedures performed at the Screening visit, which should be reported. Anticipated day-to-day fluctuations of pre-existing conditions should not be reported as AEs. Unexpected worsening of pre-existing conditions should be reported as AEs. The disease or condition being studied or expected progression,

signs, or symptoms of the disease or condition being studied such as worsening of acne should not be reported as an AE unless it is more severe than expected, results in discontinuation from the study or requires alternative therapy.

All serious adverse events (SAEs), all study product-related events, and all AEs leading to study product discontinuation must be followed until the clinical outcome is determined or until all attempts to determine resolution of the event are exhausted (not recovered is not an acceptable outcome for acute conditions). For other AEs, the status at the last visit can be entered into the eCRF.

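### Stinging, burning and itching are recalled over 14 days at Baseline but about 28 days at follow-up, and the rules that turn tolerability scores into AEs do not agree

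*Protocol*

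**What the plan says.** **Recall.** Protocol 7.6 has the investigator ask whether stinging, burning or itching occurred "since the last visit (for Visit 2 in the last 2 weeks". Section 7.10.2, item 7c, repeats the Baseline period ("has occurred on the face in the last 14 days"), and Sections 7.10.3 to 7.10.5 repeat recall since the last visit. Erythema, peeling and dryness are examined at the visit and have no recall period.

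**AE trigger in 7.6.** "An AE should be recorded if the severity is worse than at Baseline". No minimum change is stated.

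**Grading of signs in 7.6.** The investigator assesses tolerance by "examining treated areas for clinically significant non-lesional erythema, peeling, and dryness that will be graded as shown below". Table 7 defines Grade 1 dryness as "Slight barely perceptible fine superficial scale", and Grade 1 peeling in Table 6 is similarly faint.

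**AE rules in Section 8.** The investigator watches for "signs of clinically significant dryness, non-lesional erythema, and peeling and report as an AE" if worse than at Baseline. This sentence does not name stinging, burning or itching. Section 8 also says: "Anticipated day-to-day fluctuations of pre-existing conditions should not be reported as AEs". Only unexpected worsening of such a condition counts. SAP 9.3.1.1 repeats the fluctuation and worsening rules but not the 7.6 trigger.

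**Use.** SAP 3.2.1 makes the local scores and TEAEs the primary safety endpoints. Protocol 11.5.2 and SAP 9.2 tabulate scores by visit, and again without subjects who had signs or symptoms at Baseline.

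**The concern.** A longer look-back catches more episodes even when the skin has not changed. A subject with occasional itching can truthfully score 0 over 14 days and 1 over the next 28. The by-visit tables then show a rise from Baseline that comes from the question asked. The baseline-excluded table is affected too, because its subjects are cleared on 14 days and then followed on about 28. The 7.6 trigger can turn the same difference into an AE.

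The first objective is to determine DFD-03's own tolerability, and Protocol 11.1 describes the trial as providing estimates without power for a test. Absolute rates are therefore a main product of the study. Background added equally to every arm raises those rates and shrinks the DFD-03 versus Tazorac contrast.

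The second problem is that the documents do not give one rule for when a changed score becomes an AE, or state clearly when Grade 1 of a sign may be used.

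**Working it through.** The documents give no figure on this point to reproduce. The background symptom rate is not stated either, so it is an assumption below and a range is shown.

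**Step 1: recall lengths.** Protocol 7.10 sets visits at Days 1, 28 (±3), 56 (±5) and 84 (±5).
- Nominal recall: 28 − 1 = 27, 56 − 28 = 28 and 84 − 56 = 28 days, in total 83.
- Extremes: Week 4, 25 − 1 = 24 to 31 − 1 = 30; Week 8, 51 − 31 = 20 to 61 − 25 = 36; Week 12, 79 − 61 = 18 to 89 − 51 = 38.
- Baseline: 14. Follow-up recall at visits kept within window is always longer, nominally about double.

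**Step 2: size with no drug effect, per symptom.** Let p be the probability of the symptom in any 14 days, at a constant rate and independent over time. Only changes from none to any are counted.
- One follow-up visit: 1 − (1 − p)^(27/14) or 1 − (1 − p)^(28/14).
- None at Baseline and some at one or more visits, as written: (1 − p)[1 − (1 − p)^(83/14)].
- The same with 14-day recall throughout: (1 − p)[1 − (1 − p)^3].

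| Assumed p (Baseline) | One follow-up visit, as written | Above Baseline at least once, as written | Same, matched 14 days |
|---|---|---|---|
| 2% | 3.8–4.0% | 11.1% | 5.8% |
| 5% | 9.4–9.8% | 24.9% | 13.5% |
| 10% | 18.4–19.0% | 41.8% | 24.4% |
| 20% | 35.0–36.0% | 58.7% | 39.0% |

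With matched windows the expected proportion at each visit equals Baseline. The last column is not zero because three follow-up looks are set against one Baseline look. Matching removes between (58.7 − 39.0)/58.7 = 34% and (11.1 − 5.8)/11.1 = 48% of the excess.

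**Step 3: sensitivity.**
- Strong variation between subjects: a gamma frailty with shape k = 0.5 and S(t) = (1 + rt/k)^(−k), t in 14-day units and r set so that S(1) = 1 − p. S(1) − S(7) (84 days of follow-up) gives 20%, 28% and 35% at p = 5%, 10% and 20%. With matching, S(1) − S(4) gives 11%, 18% and 25%.
- A low rate: Section 8 quotes 1% to 5% for pruritus and stinging on tazarotene cream 0.1%. If 5% were a 12-week cumulative rate (no duration is given), 1 − p = 0.95^(1/6) = 0.9915, so p is about 0.85%. The results are then about 4.9% as written and 2.5% matched.

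**Step 4: effect on a contrast.** Assume drug-caused rates of 30% and 15% and an independent 24.9% background. Then 1 − 0.70 × 0.751 = 47.4% and 1 − 0.85 × 0.751 = 36.2%. The ratio falls from 2.0 to 1.31 and the difference from 15 to 11.3 points.

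**Step 5: the AE rules side by side.**
- Mild itching at Baseline, moderate at Week 4: an AE under 7.6; under Section 8 and SAP 9.3.1.1, an AE only if the worsening was unexpected. These conflict.
- New stinging after first dose, none at Baseline: an AE under 7.6 and under the general AE definition in Section 8 and the SAP. These agree, although the explicit tolerability sentence in Section 8 omits the symptom.
- New dryness: both sections require clinical significance and worsening from Baseline. These agree. However, a sign that must be clinically significant before it is graded does not fit a Grade 1 that is barely visible, so use of Grade 1 is unclear.

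**The case against.** The best defence is that the windows are the same in all four randomised arms, so no arm is favoured, and two concurrent vehicle arms show the background. Protocol 8.2 lets intermittent AEs be recorded once, SAP 9.3.4 counts a subject once per preferred term, and the study is descriptive. All of this is correct. It limits repeat counting and protects the direction of the comparison. It does not make follow-up comparable with Baseline or prevent a first background event. The vehicle arms have 25 subjects each: an observed 6/25 (24%) has a 95% Wilson interval of 11.5% to 43.4%.

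A second objection also stands. A new symptom after dosing meets the AE definition whatever the window, and AEs are also collected by diary, spontaneous report and questioning. Step 2 therefore measures shifts in scores, not TEAEs that a matched window would remove. It counts only subjects symptom-free at Baseline, so it does not measure the conflict over pre-existing symptoms either.

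Three stronger readings are tempting but not supported:
- **That all six items are affected.** The three signs have no look-back.
- **That sites following 7.6 record faint new scale as an AE while sites following Section 8 do not.** Both sections carry the same qualifier and the same comparison with Baseline for signs. Differences between sites are a risk, not something the documents show.
- **That Baseline is contaminated by washout.** The 14-day look-back equals the Table 2 washout for acne topicals and "other topical facial medication (antifungals, steroids, anti-inflammatories) on the treatment area". But 14 days is a minimum, screening may run to 60 days, and only subjects who stopped a product are exposed. Any effect would suppress AEs, opposite to the recall effect, and the documents give no basis for a net direction.

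**Conclusion.** The concern holds for stinging, burning and itching. Their recall is about twice as long at follow-up as at Baseline, so by-visit comparisons with Baseline, the baseline-excluded table and the 7.6 trigger are not like for like. With no drug effect and the constant-rate model, the proportion with a symptom at a follow-up visit would be nearly double Baseline at any low background rate. The absolute excess could be a few points or tens of points, because the documents give no background rate. The percentages are illustrations that assume constant rates; variation between subjects makes them smaller.

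The distortion is common to all arms. It inflates absolute rates and dilutes contrasts but does not reverse them.

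The AE rules conflict in a narrower way: for a pre-existing symptom that varies, with the three symptoms missing from the explicit sentence in Section 8. The qualifier in the 7.6 grading sentence is a separate defect of the scale. A reader might infer that matching the windows would cut TEAE rates from the third numerical column to the fourth; the AE definition and the other routes of AE collection do not support that.

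**What to change.** 1. Use one identical look-back at Visits 2 to 5 for every comparison of stinging, burning and itching with Baseline, including the baseline-excluded table. Keep the worst score since the last visit as a separate post-baseline incidence measure.
2. Remove the clinical-significance qualifier from the grading sentence in Protocol 7.6, so that every sign is graded 0 to 3 in every subject. Make this change together with item 3; otherwise the 7.6 trigger would reach every faint Grade 1 sign and part from Section 8 on signs as well.
3. Reconcile Protocol 7.6, Protocol 8 and SAP 9.3.1.1 into one AE reporting rule that names all six items and says how a varying pre-existing symptom is handled. Tabulate TEAEs raised only from a score change separately; no TEAE table listed in the SAP does so.

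The SAP describes the visits in the past tense. If recall can no longer be changed, the SAP should state both periods under the symptom tables, read those tables between arms at the same visit and not as change from Baseline, and add the TEAE split before lock where such events can be identified.

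Cost: one more recall item per visit, wording in two protocol sections and one SAP section, and one more table split.
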